6.0 Procedures

6.1 Data Management

The baseline and outcome-related questionnaires will be administered online via an HIPAA compliant platform such as Qualtrics or RedCap and/or via a paper collections process.

All materials collected are for research purposes only, and data will be kept in strict confidence. No information will be given to anyone without permission from the participant. The consent form includes the informed consent statement required by the University of Tennessee IRB for studies involving human subjects. This statement guarantees confidentiality and identifies the subject as the owner of the information received. Identifying information will be kept separated from study outcome data provided by participants through the use of study identification code assigned to each participant. Any identifying information that is collected on paper will be kept in a secure location within a locked file cabinet separate from the participant data charts.

Analyses will be de-identified and include only summaries of data.

6.2 Vaginal Moisturizer Distribution

Study staff will send Replens™ vaginal moisturizer to all participants. Receipt of Replens™ will be confirmed by study staff via phone call or email with participant before the agreed upon week 1 start date. The distribution of Replens™ will be tracked with a log detailing participant study ID, date product was sent to participant, date product was delivered to participant according to tracking number and date participant confirms receipt of Replens™ moisturizer.

7.0 Data Analysis

The data will be summarized using descriptive statistics (mean, standard deviation, median, percentage, and frequency). The demographic and clinical characteristics including FSFI, BITS, PROMIS SexF V2, and adverse events will be descriptively analyzed with effect size calculations done for the validated quantitative measures. All statistical analyses will be completed using either SPSS or Stata.

7.1 Analysis Plan

Aim 1: Evaluate the feasibility and acceptability of a two-component intervention for sexual function.

Feasibility will be evaluated through determining the accrual rate and screen failures. Acceptability will be determined by retention rates.

Accrual rates will be calculated by determining the number of women per month who consented to participate in the study divided by the number who were eligible and educated about the study.

For purposes of this study, screen failures will be calculated as the number of women for whom full eligibility criteria are evaluated using an eligibility checklist and initial screening call and who are determined to be ineligible through that call.

Retention will be calculated as the number of women who complete all eight weeks of the study and complete the FSFI at baseline and eight weeks divided by the number who are randomized and begin study treatment.

Conversely, attrition rates will be calculated by dividing the number of women who do not provide FSFI endpoint data for all data points by the number of women who are randomized and begin study treatment. Attrition rates of 25% or less will be considered feasible. Withdrawal reasons will be captured and reported by category.

Adherence: Adherence will be determined by calculating the number of women who begin study treatment who have at least an 80% compliance with study treatment related to the vaginal moisturizer and behavioral education materials.

This study will be determined to be feasible and acceptable if we have at least a 60% accrual rate; 80% retention rate and an 80% adherence rate (d+h under adherence).

Aim 2: Determine which measure (FSFI, ITS or PROMISE SexF) should be the primary outcome for this multi-component intervention for a larger, well powered randomized trial.

For all of the patient reported outcome measures, we will calculate missing data rates, change from baseline to each data point, and look at how variable measures are over time. This information, along with effect size data discussed in Aim 3, will be considered in determining the optimal measure to use for the primary outcome in a larger trial.

Criteria we will be looking for in a “winning” measure includes: a lack of missing data on any items; smaller “placebo” response, evidence of a better linear trend over time, and sensitivity to change.

Aim 3: Determine the effect size to be able to adequately power a larger randomized trial.

Effect sizes, Cohen's *d* or *f*, will be calculated for from baseline to week 8. Effect sizes will be calculated for both study arms for the PROMIS, FSFI total score; FSFI lubrication, pain, and desire subscales and the Impact of Treatment Scale. Means, variance, and 95% confidence intervals will also be calculated to better estimate what sample size is needed for a larger trial with at least 80% power to detect at least a medium effect size.

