4.2 Subject Recruitment

Recruitment and screening: Potential participants from the community will be identified in three ways: (1) physician referrals; (2) ResearchMatch.org; and (3) study advertisements including social media campaign, radio ads, flyers/brochures and a study website. Flyers may be posted in the greater Knoxville area. Locations such as churches, gyms, and cancer support groups. Brochures and flyers may be provided to physicians, providers, and organizations to distribute. IRB-approved recruitment materials may be posted on social media or in University of Tennessee/non-University of Tennessee newspapers, newsletters or websites, or read over WUOT. Participant eligibility will be determined using the Screening Eligibility Check List created from the criteria listed in 4.3.

Baseline visit: If a woman is screened eligible using the screening eligibility checklist, she will be mailed or emailed the consent form and scheduled for a virtual baseline visit. Baseline visits will be conducted using a HIPAA compliant platform (video or phone). The purpose of the baseline visit is to ensure that participants understand the study requirements, have their questions answered, be consented, complete baseline questionnaires, and are randomized. After confirming eligibility and reviewing the consent, eligible women will sign the consent using an IRB approved e-consent platform. After consent is attained, participants will be given a study number. Then baseline questionnaires will be completed, women will be randomized to vulvovaginal treatment with hypnosis starting in two weeks or vulvovaginal treatment control. Randomization will be done at the time of consent using a random number generator with “1” being the intervention group and “2” being the control group. They will then be educated about treatment with a vaginal moisturizer (see intervention details below). This treatment will begin within two weeks of completing the baseline visit (to allow for shipping of the moisturizer) and will be verified with the study coordinator. The start of vulvovaginal treatment will be confirmed by the study coordinator either through an email or phone communication with the participant. After confirmation of the start of vaginal moisturizer treatment, behavior education visit (Intervention) or follow up phone call (Control) will be planned for two weeks (+/- 3 days) for both groups.

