Perform a hypnotic induction to focus on improving body-image; suggestions for visualizing a body as strong, healthy, and beautiful. Used during study weeks 5 and 6.

Goals:

- Increase relaxation

- Build on positive feelings about your body
- Improve feelings about your sexuality
- Improve sexual experience

Audio III: Hypnotic relaxation for sexual desire and energy

Perform a hypnotic induction to improve desire for intimacy and experience increased energy and sense of wellbeing. Used during study weeks 7 and 8.

Goals:

- Increase relaxation
- Build upon improved feelings about your body
- Build upon improved feelings about your sexuality
- Improve sexual desire and energy

VVA Control

The VVA control group will get the eight weeks of vaginal moisturizer exactly as described above for the intervention group. After completion of the eight weeks of the study, the women assigned to the VVA control will be offered the Hypnotic Relaxation Intervention to complete on their own off study.

Accrual: Our research team has successfully recruited cancer survivors into clinical trials with an average of 4-6 per month. Weekly and monthly accrual goals will be set and achieved through a multipronged recruitment approach.

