5.0 Measures

Feasibility: We will keep spreadsheets of the numbers of women who receive a full eligibility screen and how many of those are found eligible versus not eligible, and of those eligible, how many consent to participate versus decline participation. The analysis and definition of what is considered feasible is in the statistical analysis section.

Acceptability: We will keep records of the number of women who complete the protocol, including the questionnaires at all data points versus those who do not complete either the protocol treatment, the questionnaires, and/or both. The analysis and definition of what is considered feasible is in the statistical analysis section.

Adherence: We will keep the following data to determine adherence to various aspects of the study: a) Number of missing questions within questionnaires; b) number and type of missing questionnaires; c) number of women who use the moisturizer exactly per protocol; d) number of women who use the moisturizer at least 80% of the time described by the protocol; e) number of women who use the moisturizer less than half of the time described by the protocol; f) number of women in each arm who listen to each audio sessions at least once in the assigned two week period; g) number of women in each arm who listen to each audio session at least once per week; h) number of women in each arm who listen to each audio session more than once per week.

Demographic Information Form: a brief medical history that obtains age, gender, sexual orientation, race/ethnicity, education level, marital status, cancer diagnosis, and similar demographic information. In addition, any other medical conditions that would exclude possible participants will be captured with this form.

Hypnosis Practice Log: Frequency of home practice is thought to be one of the moderators of the efficacy of hypnosis interventions.⁵² Participants in the hypnosis group will be given a log to be completed weekly. The log will provide space to put the date, whether or not the participant listened to their audio recording, the number of times they practiced, and provide a space for comments about any interruptions or barriers to listening to the recordings.

Current topical (e.g. lidocaine or vaginal moisturizer) products will ask which products (if any) participants used vaginally within the last 2 weeks.

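### The accrual rate that must reach 60% divides a monthly count by an undated count, over a denominator that rests on an undefined term

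*Combined protocol and SAP*

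**What the plan says.** Section 7.1 (Aim 1) evaluates feasibility through the accrual rate and screen failures. It defines the accrual rate as the "number of women per month who consented to participate in the study divided by the number who were eligible and educated" about the study. No period is attached to the denominator, and the term for having been educated is not explained.

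The same section ends Aim 1 with a decision rule that requires "at least a 60% accrual rate; 80% retention rate and an 80% adherence rate". All three must hold.

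Four other places bear on this:

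- Section 5.0 (Feasibility) keeps counts of women screened and found eligible and, "of those eligible, how many consent to participate versus decline participation". It refers to the statistical section for the definition of feasible.
- Section 4.2 says that once a woman is screened eligible, "she will be mailed or emailed the consent form and scheduled for a virtual baseline visit". Making sure that she understands the requirements, answering her questions and taking consent all belong to that visit. The Screening and Enrollment Log described there lists eligibility status, screening and consent dates, and referral source.
- Section 4.4 (Accrual) reports the team's past recruitment as "an average of 4-6 per month".
- Section 7.2 plans 15 participants per arm.

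**The concern.** A percentage threshold needs a proportion, with numerator and denominator counted over the same women and the same period. Here one is a monthly flow and the other is a count with no stated period. An analyst who follows the sentence as written gets a number that shrinks as recruitment lasts longer, whatever share of women agree to join.

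The denominator raises a second question. If a woman counts as educated only once she attends the baseline visit, those who are eligible but do not book or do not attend are left out. Those losses are part of what a feasibility measure should show.

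Accrual is one of three conditions that must all hold for the conclusion on the primary aim. An unclear definition here can therefore change the stated result of the study.

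**Working it through.** **Inputs from the documents.** Threshold 60% (7.1). Planned sample 2 × 15 = 30 (7.2). Pace 4 to 6 women per month (4.4).

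**Assumptions.** The number consenting is taken as 30, since consent and randomization fall in the same visit. The past pace is taken to carry over. The documents give no expected number of eligible or educated women, so 40 to 60 is used as an illustrative range.

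The plan gives no derivation for 60%, so there is no figure of its own to reproduce.

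**Step 1: the literal formula.** Let C be total consents, T the months of recruitment and D the total in the denominator. The sentence gives (C/T)/D, which is uptake (C/D) divided by T.

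- Duration: 30/6 = 5 months to 30/4 = 7.5 months.
- Best possible case, with every woman in the denominator consenting (D = 30): 4/30 = 13% to 6/30 = 20%.
- To reach 60% with complete uptake, T must be at most 1/0.60 = 1.67 months. That is 30/1.67 = 18 women per month, three times the upper end of the cited pace.

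**Step 2: both counts per month.** The unit problem goes away, but this yields one rate for each month. The text does not say whether a pooled rate, the mean of the monthly rates or each month's rate is compared with 60%. As an invented six-month example, take consents of 2, 3, 5, 6, 7, 7 among 2, 3, 8, 9, 9, 9 women. The pooled rate is 30/40 = 75%. The mean of the six monthly rates is 81%. Both pass here, so in this example the choice changes the reported figure but not the conclusion.

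**Step 3: the denominator, with one common period.** With 30 consents, the 60% line is met only if the denominator is 30/0.60 = 50 or fewer.

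| Denominator (assumed) | Rate | Against 60% |
|---|---|---|
| 40 eligible and educated | 30/40 = 75% | met |
| 50 | 30/50 = 60% | just met |
| 60 eligible | 30/60 = 50% | not met |

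The definition decides the outcome whenever the educated count is 50 or fewer and the eligible count is above 50. If the two counts are the same, the definition makes no difference.

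**Step 4: can the denominator be counted?** The eligible total and the consent total are both kept under 4.2 and 5.0. A count of women educated about the study is not among the items listed in either place.

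**The case against.** The strongest reply is that nobody would apply the formula literally. A 60% threshold only makes sense for a proportion, and the section speaks of rates in the plural, so consents in a month over women informed in that month is a natural reading. The very low ceiling in Step 1 itself shows that a mixed-period ratio was not meant. This stands as to intent. It does not supply the missing period, and it leaves the choice between pooled and monthly rates open.

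A reader might infer that Section 5.0 sets a competing accrual rate over all eligible women. It does not. It lists counts to be kept and defers to the analysis section, and recording more than the analysis uses is no contradiction.

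A reader might also infer that the plan restricts the denominator to women who reach the baseline visit. That is plausible from 4.2 but is not stated. The screening call, or the consent form sent in advance, could equally count as education, in which case nearly all eligible women stay in. The schedule in 4.5 has a row for study education, but its marks are not legible in the text available, so nothing is rested on it.

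Consent among women who were informed is also a legitimate measure of uptake. Moving the 60% to all eligible women makes the condition stricter. That is a fair point for the sponsor to weigh, and the fix leaves room for it.

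Finally, this is a 30-woman pilot, and the hypothesis in Section 1.0 concerns 80% completion rather than accrual. The decision rule in 7.1 nonetheless makes accrual a condition of the overall conclusion.

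**Conclusion.** Wrong as written. Applied literally at 4 to 6 women per month and 30 women, the accrual condition tops out at 13% to 20% and cannot reach 60%. That result uses only the protocol's own figures, with the pace assumed to carry over. A proportion was evidently meant, but the text does not define it fully: the period is missing, and so is the choice between a pooled and a monthly rate.

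The denominator point is weaker in evidence but could matter more in practice. The term is undefined and is not among the listed log fields. Under one plausible reading it inflates the rate. The 75% against 50% contrast rests on assumed counts of 40 and 60. It shows that the definition can move the result across the threshold, not that it will.

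The documents do not support the further inference that the sponsor would pick a reading once the counts are known. The definition should be settled beforehand so that the question does not arise.

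**What to change.** Replace the accrual sentence in Section 7.1 with: *Accrual rate = total women who consent divided by total women found eligible on the screening checklist, both over the whole recruitment period.* Apply the 60% threshold to this figure. Report women consented per month separately, as a pace with no percentage threshold.

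If the sponsor prefers to keep education in the denominator, 7.1 should name the step that counts (for example, the screening call) and state the common period and that the rate is pooled. The log should record that step, and the all-eligible proportion should be reported alongside.

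The main fix costs one sentence and no new data, since 4.2 and 5.0 already provide for the counts. The alternative needs one more log field. The downside is that the all-eligible rate may be less favourable than one limited to women who were educated about the study.

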1.0 Objectives/Specific Aims

Primary Aim: Evaluate the feasibility and acceptability of a multi-component intervention for sexual function.

Hypothesis: At least 80% of randomized participants will complete the study without differential withdraws from the VVA control group.

Exploratory Aims:

Aim 2: Determine which measure (FSFI, ITS or PROMIS SexF) should be the primary outcome for this multi-component intervention for a larger, well powered randomized trial.

Aim 3: Determine the effect size to be able to adequately power a larger randomized trial.

This study is related to an NCI Moonshot priority (F) to minimize the debilitating side effects of cancer treatment. Completion of these aims will provide a critical foundation for NCI Cancer Prevention and Control Clinical Trials Grant Program R01 submission to implement a phase II or III randomized trial to implement in the NCORP network.

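### The 80% retention criterion counts only women who begin treatment, and no by-arm withdrawal comparison is planned, so the primary hypothesis is answered only in part

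*Combined protocol and SAP*

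**What the plan says.** Section 1.0 gives the hypothesis for the primary aim: "At least 80% of randomized participants will complete the study without differential withdraws from the VVA control group". It has two parts, a completion rate among all randomized women and a condition on how the arms compare.

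Section 5.0 refers the reader to the statistical section for what counts as feasible. There, section 7.1 (Aim 1) sets these rules:

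- Retention: women who finish the eight weeks and give the FSFI at baseline and week 8, "divided by the number who are randomized and begin study treatment".
- Attrition: women without complete FSFI endpoint data, divided "by the number of women who are randomized and begin study treatment".
- Adherence: "Adherence will be determined by calculating the number of women who begin study treatment who have at least an 80% compliance" with the study treatment.
- Accrual: the number of "women per month who consented to participate in the study divided by the number who were eligible and educated about the study".
- Decision: feasible and acceptable with at least 60% accrual, "80% retention rate and an 80% adherence rate (d+h under adherence").
- Withdrawals: "Withdrawal reasons will be captured and reported by category".

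Section 4.2 places randomization at the baseline visit and lets the moisturizer start up to two weeks later, because it has to be shipped. Section 7.2 plans 15 women per arm.

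**The concern.** The hypothesis and the rule meant to judge it use different populations. A woman who is randomized and then lost before her first application is a failure under section 1.0 but is in neither the numerator nor the denominator of retention and attrition under 7.1. The other two criteria do not count her as a loss either: adherence is restricted to women who begin treatment, and accrual counts her as a success because she consented.

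The between-arm condition appears only in section 1.0. Section 7.1 gives a single 80% figure, which I read as pooled over arms, and withdrawal reasons by category. Reporting by arm is stated for audio use (section 5.0, items f to h) and for effect sizes (section 7.1, Aim 3), but not for retention or withdrawal. The term differential is not defined.

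Retention is the plan's stated measure of acceptability, which is half of the primary aim, and the result is meant to support a larger trial. A report that follows 7.1 to the letter could declare the retention criterion met when the hypothesis is false, and would contain no planned result on whether the arms lost women at different rates.

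**Working it through.** **Inputs.** Threshold 80% (sections 1.0 and 7.1). N = 30, from 15 per arm in 7.2; that section does not say whether 15 means randomized or started, so 30 randomized is an assumption. The documents give no start or completion rates. There is no stated figure to reproduce, because 80% is a chosen threshold.

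**1. Denominator.** With k non-starters there are 30 − k starters. The fewest completers that pass 7.1 is 0.80 × (30 − k), rounded up. The hypothesis needs 0.80 × 30 = 24.

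| Non-starters | Fewest completers to pass 7.1 | Rate among starters | Rate among randomized | Hypothesis rate met? |
|---|---|---|---|---|
| 0 | 24 | 24/30 = 80.0% | 80.0% | yes |
| 1 | 24 | 24/29 = 82.8% | 80.0% | yes |
| 2 | 23 | 23/28 = 82.1% | 76.7% | no |
| 3 | 22 | 22/27 = 81.5% | 73.3% | no |
| 4 | 21 | 21/26 = 80.8% | 70.0% | no |
| 5 | 20 | 20/25 = 80.0% | 66.7% | no |

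The two denominators can give different answers from the second non-starter on.

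**2. How often that would happen.** Let each randomized woman start with probability s, and each starter complete with probability c. Sum the binomial probabilities of m starters out of 30 and x completers out of m over all outcomes with x/m ≥ 0.80 and x < 24. Both rates are assumed, so a range is shown:

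| Completion among starters, c | s = 98% | s = 95% | s = 93.3% | s = 90% |
|---|---|---|---|---|
| 85% | 2.7% | 13% | 21% | 36% |
| 90% | 1.4% | 8.4% | 14% | 29% |
| 95% | 0.2% | 2.1% | 4.5% | 13% |

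These are chances that the retention criterion passes with fewer than 24 of 30 randomized women completing. They say nothing about accrual or adherence.

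**3. By arm.** Take 15 + 15 with everyone starting. Retention of 12/15 and 12/15 gives 24/30 = 80%, a difference of 0 points. Retention of 15/15 and 9/15 also gives 24/30 = 80%, with a difference of 100% − 60% = 40 points. The criterion returns the same result for both.

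**4. What a by-arm comparison could show.** At 12/15 v 12/15, the exact unconditional (score-based) 95% confidence interval for the difference is about −31 to +31 points. Fisher's exact test at 15 per arm has power of about 33% for 90% v 60% completion. Estimation is realistic at this size; a test is not.

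**The case against.** Four points deserve weight.

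- If every randomized woman starts, the 7.1 rate is exactly the hypothesis rate, and one non-starter in 30 does not change the result. This stands. A reader might infer that 7.1 evaluates neither part of the hypothesis, but the documents do not support that: the first part is evaluated correctly when start-up loss is negligible.
- A starters' denominator is defensible for judging how acceptable the treatment is to women who try it. This stands as a case for reporting that rate. It does not remove the conflict with section 1.0, which names randomized women.
- Section 1.0 itself commits to looking at the arms, completion and withdrawal reasons are recorded, and section 9.0 reviews retention. So the data will exist, and it would be wrong to infer that differential withdrawal cannot be examined. What is missing is a statement of the analysis.
- The adherence criterion offers some protection. Item d counts the "number of women who use the moisturizer at least 80% of the time described by the protocol", and controls use the same moisturizer, so women who start and leave early may count against it. How much this helps cannot be calculated. Section 7.1 does not say how items d and h combine, or how controls, who have no audio on study, are judged. A reader might turn the probabilities above into chances of wrongly declaring the study feasible and acceptable. The documents do not support that step, because the declaration also depends on the accrual and adherence criteria.

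**Conclusion.** The concern holds in a limited form. The 80% criterion agrees with the first part of the primary hypothesis only if almost every randomized woman starts treatment; from 2 non-starters in 30 it can pass when the hypothesis rate is missed. The second part, no differential withdrawal, has no stated analysis, and this is so whatever the number of non-starters.

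The counts rest only on 30 randomized and, for the arm example, on an equal split. The probabilities also rest on assumed start and completion rates, and run from 0.2% to 36% over the range shown, so they illustrate the problem and do not predict it. That the single retention figure is pooled is inferred from its being the only one given. This should be corrected before analysis, but it does not call the design or the data collection into question.

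**What to change.** In section 7.1:

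1. Apply the 80% retention criterion, and calculate attrition, over all randomized women, as section 1.0 states. Report the rate among women who began treatment as secondary, with the number of non-starters in each arm.
2. Report retention and withdrawal, with reasons, by arm. Give the between-arm difference in proportions with an exact 95% confidence interval, as an estimate and not a test, and base any statement on differential withdrawal on it. State that about 15 per arm cannot exclude a sizeable difference. Proportions are preferable to counts because section 4.2 describes a random number generator and states no blocking, so the arms may be unequal.

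This needs wording only. Arm and completion are recorded, and section 4.2 has the coordinator confirm each woman's treatment start. Item 2 changes no threshold. Item 1 has a real cost: if some women never start, reported retention is lower and the criterion is harder to pass. At a 93.3% start rate, the chance of passing the retention criterion falls from 0.78 to 0.57 with 85% completion among starters, and from 0.95 to 0.81 with 90%.

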4.5 Time and Events Table

Table 2. Schedule of Participant Activities (All study contact is virtual)

Activities			Treatment and Assessments							
	Screening	Baseline	Wk 1	Wk 2	Wk 3	Wk 4	Wk 5	Wk 6	Wk 7	Wk 8
Study Education										
Consent										
Screening Check List										
Demographic Information Form										
Outcomes										
Female Sexual Function Index full scale										
FSFI subscales: pain, dryness, desire		Included in full scale								Included in full scale
Impact of Treatment Scale										
PROMIS® Sexual Function and Satisfaction										
Current vaginally applied topical products										
Hypnosis practice log					*	*	*	*	*	*
Adverse Events										
Follow up Phone Calls										
Conditions										
Intervention		Vaginal Moisturizer								
		Hypnosis								
VVA Control		Vaginal Moisturizer								

* Intervention group only

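### Retention and attrition in 7.1 are presented as converses but are not complements, so the 80% retention rule and the separate 25% attrition limit can disagree on the same women

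*Combined protocol and SAP*

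**What the plan says.** The governing text is in 7.1 Analysis Plan, under Aim 1.

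- **Retention.** The numerator is the "number of women who complete all eight weeks of the study and complete the FSFI at baseline and eight weeks". The denominator is the randomized women who start treatment.
- **Attrition.** As the converse, "attrition rates will be calculated by dividing the number of women who do not provide FSFI endpoint data for all data points". The denominator is the same as for retention. Attrition of at most 25% is then described as feasible.
- **Go rule.** The study is feasible and acceptable with at least 60% accrual, 80% retention and 80% adherence. Attrition is not part of this rule.

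Four other places bear on it:

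- 5.0 Measures says the acceptability records will hold the "number of women who complete the protocol, including the questionnaires at all data points". It refers to the statistical section for the definition, and 7.1 says that acceptability is judged by retention.
- The schedule in 4.5 has a separate row, "FSFI subscales: pain, dryness, desire", noted as part of the full scale at baseline and at week 8. The marks for the weeks between are not legible in the text available to us.
- In 7.1, Aim 2 plans change from baseline at every data point and prefers a measure with a more linear trend. Aim 3 computes effect sizes from baseline to week 8 only.
- 7.2 lists both retention and attrition among the main outcomes, with 15 women per arm.

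No section says which FSFI data points the attrition sentence means.

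**The concern.** The attrition sentence opens "Conversely, attrition rates will be calculated by dividing", and the denominators match, so a reader expects the two rates to sum to 100%. They need not, for two reasons. Retention requires finishing all eight weeks and attrition does not. Retention names two FSFI assessments, while attrition asks for all of them without saying which they are.

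Both rates are main outcomes and each has its own numerical limit. With about 30 women, one or two classifications can move a rate across its limit. A skipped form could be reported as a lost participant. If the wording stays open, the choice of reading could also be made after the counts are known.

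**Working it through.** The plan gives no formula behind 15 per arm or behind the limits, so there is no figure to reproduce. The check counts women at n = 30 (7.2), assuming that all 30 start treatment.

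**1. Limits as counts.**
- Retention passes at 0.80 × 30 = 24 women or more.
- Attrition passes at 0.25 × 30 = 7.5, so at most 7 women (23.3%). Eight women (26.7%) fail.

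**2. Reading A: interim FSFI subscale forms count as data points.** Let R be the number retained and K the number of those who miss an interim form. Assume that every non-retained woman lacks some FSFI data. Then attrition = (30 − R + K)/30, and the two rates sum to 1 + K/30. Attrition fails once 30 − R + K reaches 8, that is, once K = R − 22.
- R = 24, K = 2: retention 24/30 = 80.0% (pass); attrition (6 + 2)/30 = 26.7% (fail); sum 106.7%.
- R = 27, K = 5: retention 90.0% (pass); attrition (3 + 5)/30 = 26.7% (fail); sum 116.7%. With K = 4, attrition is 7/30 = 23.3% and there is no split.
- R = 30, K = 8: retention 100% (pass); attrition 26.7% (fail).

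**3. How easily this could happen under Reading A.** These inputs are assumptions, not figures from the plan. With 10% true dropout and three interim forms, each missed independently with probability m, expected attrition is 1 − 0.9 × (1 − m)³:
- m = 0.05: 22.8%
- m = 0.07: 27.6%
- m = 0.10: 34.4%

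Expected retention stays at 90% throughout. Next, take true retention of 80% to 95%, one or three interim forms, and each form completed 90% or 95% of the time. The exact binomial probability that retention passes while attrition fails then runs from 0.6% (95% retention, one form, 95% completed) to 84% (90% retention, three forms, 90% completed). The range is too wide to serve as a forecast. It shows only that the result depends on interim form completion, which retention ignores.

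**4. Reading B: only baseline and week 8 count.** No woman can be in both groups. A woman who does not complete all eight weeks but returns both FSFIs is in neither. As an illustration, suppose 8 such women and 22 full completers: retention is 22/30 = 73.3% (fail) and attrition is 0/30 (pass).

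**5. One shared definition, limits unchanged.** With attrition = 1 − retention, 23/30 retained gives 76.7% (fails 80%) and attrition 7/30 = 23.3% (passes 25%). The same occurs at every n from 24 to 29. For example, 19/25 gives 76.0% and 24.0%, and 22/29 gives 75.9% and 24.1%. Aligning the definitions removes the misclassified women but not the split verdict.

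**The case against.** The best defence is that the attrition sentence directly follows one naming baseline and week 8, speaks of endpoint data, and is offered as the converse. On that view its data points are those two, which fits the baseline-to-week-8 effect sizes of Aim 3, and nobody is counted twice. This is a fair reading, and the lost schedule marks mean that Reading A cannot be proved. Reading A nevertheless has support. A separate subscale row noted as part of the full scale at the two ends has little purpose unless the subscales are also given alone in between. Linearity of a trend also cannot be judged from two points.

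Reading B does not rescue the text, because the eight-week condition still appears in only one definition. It can be said that a woman who stops treatment but stays to give the week-8 FSFI has completed the study, which would shrink the neither group. That is plausible, but the plan does not say so.

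The examples in the working are also illustrations, and the two-weekly calls in 4.2 are meant to secure data completion. Both points stand. They limit how likely a split is, but not whether the definitions match.

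A reader might go further and take 5.0 as a third competing definition. The documents do not support that: 5.0 describes records to be kept and defers to the statistical section, where 7.1 ties acceptability to retention.

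**Conclusion.** The point holds and should be corrected, within limits. The two definitions are not complements on either reading of the data points. That the same woman can be both retained and lost depends on interim FSFI forms counting, which is likely but not established. That a woman can be in neither group depends on how completing eight weeks is read. The mismatch between 80% and 25% depends on neither.

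A reader might infer that the primary aim can pass and fail at once. The text does not support this. The go rule uses retention alone, and retention names its two FSFI time points, so a missed interim form cannot change that rule's result. The disagreement is between the go rule and the separate statement that attrition up to 25% is feasible. At n = 30 and exactly 80% retention, two missed interim forms are enough to produce it under Reading A.

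**What to change.** In 7.1:

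- Define one completion event: the woman completes the eight-week study period, whether or not she stopped treatment early, and provides the week-8 FSFI. The baseline FSFI need not be part of the event, because 4.2 has baseline questionnaires completed at the baseline visit, before treatment starts.
- Define retention as the proportion with that event, and attrition as 1 − retention over the same denominator.
- State one complementary cut-off. The go rule's 80% retention implies 20% attrition, which replaces the 25% statement.
- Report missed interim forms only as data completeness, under adherence items a and b of 5.0.
- Report women who stop treatment but give week-8 data as a separate count.

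In 5.0, add a cross-reference so that the acceptability record points to the same event.

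The cost is wording only. No new data are needed and the sample size is unaffected. The change should be dated and made before retention counts are reviewed.
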